5.4 Blinding and procedures for unblinding the study

5.4.1 Methods for ensuring blinding

The Sponsor, Clinical Research Organization, Investigators, study staff participating in patient care or clinical evaluations, and patients will be blinded to study drug assignment until all patients have completed the study and the database is locked. Unblinded pharmacy staff or unblinded study staff (not participating in patient care) will be responsible for maintaining accountability and preparing the blinded study drug, ensuring all infusion bags or bottles are appropriately labelled and masked according to the Pharmacy Manual. The 600-mg dose of ceftriaxone fosamil (for modified dose, see Section 5.5.3) infused over 60- minutes is split in this study into two 300-mg infusions over 30 minutes each q12h ($\pm 2h$). The 2 grams dose of IV ceftriaxone is infused over 30 minutes followed by IV saline placebo infused over 30 minutes q24h ($\pm 2h$). Twelve hours after the infusions of the IV ceftriaxone and IV saline placebo (ie, between IV ceftriaxone/IV placebo infusions) patients in the ceftriaxone group will receive two consecutive IV saline placebo infusions, each infused over 30 minutes q24h ($\pm 2h$). The ceftriaxone and placebo infusions will correspond with the q12h ($\pm 2h$) ceftriaxone infusions thus maintaining the blind.

The Sponsor or Clinical Research Organization will assign an unblinded monitor to confirm drug accountability.

5.4.2 Methods for unblinding the study

Individual treatment codes, indicating the treatment randomisation for each randomised patient, will be available to the investigator(s) from the IVRS/IWRS. Routines for this will be described in the IVRS/IWRS user manual that will be provided to each centre.

The treatment code should not be broken by the investigator or blinded study staff except in medical emergencies when the appropriate management of the patient requires knowledge of the treatment randomisation. If the blind is broken, the date, the time, and the reason must be documented /recorded via IVRS/IWRS and in any associated AE report. The investigator is responsible for ensuring this documentation is maintained and reports the action to AstraZeneca, without revealing the treatment given to the patient to the blinded AstraZeneca staff.

AstraZeneca retains the right to break the code for Serious Adverse Events (SAEs) that are unexpected and are suspected to be causally related to an investigational product and that potentially require expedited reporting to regulatory authorities. Treatment codes will not be broken for the planned analyses of data until all decisions on the evaluability of the data from each individual patient have been made and documented.

5.5 Treatments

5.5.1 Identity of investigational product(s)

5.5.1.1 Ceftaroline fosamil for injection

Ceftaroline fosamil for injection is supplied as 600 mg of the prodrug of ceftaroline, a sterile pale yellowish-white to light yellow crystalline powder in a single-dose, clear glass 20 mL vial. An excipient, L-arginine (approximately 660 mg L-arginine/g of ceftaroline prodrug), is added as an alkalisng agent to control pH of the constituted solution to pH 4.8 to 6.2. The product is limited to investigational use only. Please refer to the current IB for additional information.

For IV administration, Ceftaroline fosamil for injection is constituted with 20.0 mL of sterile water for injection; the entire contents of the resulting solution are transferred to an infusion bag/bottle containing sterile sodium chloride 0.9% for dilution of the infusion. Please refer to the Pharmacy Manual for detailed information on study drug preparation.

5.5.1.2 Ceftriaxone for injection

Ceftriaxone for Injection is supplied as 1 g/vial (2 vials for a 2 grams dose) using commercially available material. Consult the local product information regarding administration, warnings, precautions and AEs reported with the use of ceftriaxone. Refer to the Pharmacy Manual for information regarding formulation and preparation of ceftriaxone.

Table 3 Investigational product

Investigational product	Dosage form and strength	Manufacturer
Ceftaroline fosamil	Powder for Intravenous Solution, 600 mg	
Ceftriaxone	Powder for Intravenous Solution, 1 g/vial	

5.5.2 Doses and treatment regimens

Patients are required to be hospitalised during treatment with study drug.

5.5.2.1 Ceftaroline fosamil

Patients randomised to ceftaroline fosamil will receive 600 mg IV q 12h (\pm 2h), infused over 60 (\pm 20) minutes for 5 to 7 days. To maintain study blinding, each 60-minute infusion will be divided into 2 sequential 30 (\pm 10) min infusions containing 50% of the total dose. The individual infusion bags/bottles will be administered in immediate succession (see [Table 4](#)).

5.5.2.2 Ceftriaxone

Patients randomised to receive IV ceftriaxone will receive a dose of 2 g infused over 30 (\pm 10) min immediately followed by IV saline placebo infused over 30 (\pm 10) minutes, q24h (\pm 2h) for

5 to 7 days. Twelve hours after each dose of ceftriaxone and saline placebo (ie, between ceftriaxone doses), patients in this group will receive two consecutive saline placebo infusions, each infused over 30 (± 10) minutes q24h (± 2 h). The ceftriaxone and saline placebo infusions will correspond to the q12h (± 2 h) infusions of ceftaroline, thereby maintaining the blind (see Table 4).

Table 4 Study Drug Dosing Overview in Patients with Normal Renal Function

Treatment Group	First Daily Dose		Second Daily Dose	
	Infusion 1	Infusion 2	Infusion 1	Infusion 2
	30 (± 10) min	30 (± 10) min	30 (± 10) min	30 (± 10) min
Ceftaroline fosamil	Ceftaroline 300 mg	Ceftaroline 300 mg	Ceftaroline 300 mg	Ceftaroline 300 mg
Ceftriaxone	Ceftriaxone 2 g	Placebo	Placebo	Placebo

5.5.3 Dose Adjustment

5.5.3.1 Ceftaroline fosamil

At any time, (including Day 1), the dose of ceftaroline fosamil may be adjusted by unblinded pharmacy staff or unblinded study staff to 2 consecutive infusions of ceftaroline fosamil (200 mg) each infused over 30 min (± 10 min) q12h (± 2 h) for patients with moderate renal impairment ($30 \text{ mL/min} < \text{CL}_{\text{CR}} \leq 50 \text{ mL/min}$), as estimated by the Cockcroft-Gault formula. At any time, the dose of ceftaroline fosamil may be readjusted to 2 consecutive infusions of ceftaroline fosamil (300 mg) each infused over 30 min (± 10 min) q12h (± 2 h) when renal function improves ($\text{CL}_{\text{CR}} > 50 \text{ mL/min}$).

If, at any time a patient's estimated CL_{CR} is less than or equal to 30 mL/min during treatment contact the AstraZeneca study physician.

5.5.3.2 Ceftriaxone

It is not necessary to adjust the dose of ceftriaxone for patients with mild ($50 \text{ mL/min} < \text{CL}_{\text{CR}} \leq 80 \text{ mL/min}$) or moderate ($30 \text{ mL/min} < \text{CL}_{\text{CR}} \leq 50 \text{ mL/min}$) renal insufficiency.

If at any time a patient's estimated CL_{CR} is less than or equal to 30 mL/min during treatment, contact the AstraZeneca study physician.

5.5.4 Labelling

Labels will be prepared in accordance with Good Manufacturing Practice (GMP) and local regulatory guidelines. The labels will fulfil GMP Annex 13 requirements for labelling. Patient kit label text will be translated into local language.

The vial labels will be labelled with a minimum of the following information:

- Study Code
- Kit ID number
- Drug name, Dosage form, Dosage quantity
- Route of administration
- Storage conditions
- Sponsor name
- Space to complete the following:
 - Enrolment Code
 - Date of Administration

Please refer to the Pharmacy Manual for the information contained on the label attached to the infusion bag/bottle.

5.5.5 Storage

All study drugs must be kept in a secure place under appropriate storage conditions as indicated below. For additional information please refer to the Pharmacy Manual.

5.5.5.1 Ceftaroline fosamil

Vials of ceftaroline fosamil for injection dry mixture should be stored refrigerated at 2°C to 8°C until ready for use. Constituted and diluted ceftaroline fosamil IV infusion bags / bottles should be administered promptly. For additional storage information, please refer to the Pharmacy Manual.

5.5.5.2 Ceftriaxone

Ceftriaxone should be stored in accordance with local product information.

5.6 Concomitant and post-study treatment(s)

All antimicrobial and non-antimicrobial therapy administered within 4 weeks prior to baseline will be documented in the electronic case report form (eCRF). Patients who received systemic antimicrobial therapy (see [Appendix F](#)) for the treatment of the current CABP within 96 hours prior to study randomisation will be excluded from the study unless they meet the specific criteria delineated in Section 4.

Concomitant systemic antimicrobial agents are not permitted and their use, for any reason other than the patient being considered a treatment failure, must be discussed with the AstraZeneca study physician before administration.

The use of probenecid is not allowed within 3 days prior to dosing with study drug therapy or during the period of time encompassing administration of study drug therapy.

Other medication, which is considered necessary for the patient's safety and well being, may be given at the discretion of the investigator and recorded in the appropriate sections of the Case Report Form.

5.7 Treatment compliance

The administration of all study drugs (including investigational products) should be recorded in the appropriate sections of the eCRF.

The blinded investigator or blinded medically qualified delegate will administer the blinded study drug and record the date, time, specific infusion number and volume infused, or check a box if the infusion was missed. This information will be verified by the blinded monitor at monitoring visits. This will assure treatment compliance.

All used (partially or completely infused) and unused infusions bags/bottles must be returned to the pharmacy. It is the responsibility of the blinded monitor to ensure these are returned, and the unblinded monitor to perform accountability.

5.7.1 Accountability

Study drug will be dispensed to, and administered by, the blinded investigator or blinded medically qualified delegate (as documented per local requirements in the CSA), by the unblinded site pharmacist or unblinded study staff. Records of study drug usage should include the identification of the person to whom the study drug was administered, the quantity and date of administration, and a record of unused or partially used study drug. The unblinded pharmacist or unblinded study staff is responsible for maintaining accurate study drug accountability records throughout the study. Each administration of study drug will be documented in the eCRF.

Additionally, it is the blinded investigator's responsibility to ensure that a process for handling blinded and unblinded study treatments is established. This includes but is not limited to:

- Deliveries of such products are correctly received by a responsible person (eg, pharmacist)
- Deliveries are recorded
- Study drug is handled and stored safely and properly
- Study drug provided for this study are used only as directed in the study protocol
- Appropriate unblinded study personnel and the unblinded study monitor account for all drugs received at the site, dispensed for the patient, and returned to the

pharmacy. Any discrepancies should be documented, investigated, and appropriately resolved

- At the end of the study, after accountability has been performed and documented, site personnel account will arrange for appropriate destruction or return of all partially used or unused drugs to a designated facility or AstraZeneca for destruction. It must be possible to reconcile delivery records with records of study drug use and destroyed/returned stock. The unblinded pharmacist should sign certificates of delivery and return.

The drug accountability will be verified by AstraZeneca's unblinded study monitor or designee during on-site monitoring visits. Infusion bags will be disposed of according to hospital regulations. Empty vials should be retained. Contents of the study drug containers must not be combined.

Refer to the Pharmacy Manual for additional information.

5.8 Discontinuation of investigational product

Patients may discontinue study drug at any time. Those patients who discontinue prematurely from the study treatment regimen should always be asked about the reason(s) and the presence of any AE(s). The EOT assessments should be performed on the last day the study treatment regimen is administered and all other visits occurring after the EOT should be performed, (see [Table 1](#)). AE(s) should also be followed, as appropriate (see Section [6.4.3](#) and [6.4.4](#)).

The following reasons for premature discontinuation of study drug may include, but are not limited to:

- Patient decision. The patient is at any time free to discontinue treatment, without prejudice to further treatment
- Severe non-compliance to study protocol
- Safety
 - Occurrence of an AE that, in the opinion of the Investigator, warrants the patient's permanent discontinuation from study drug therapy
 - Suspected or confirmed pregnancy (see Section [13.3](#)) or nursing during the study drug administration period. Female patients whose pregnancy test is positive at the EOT visit must be followed through the immediate postnatal period or until termination of the pregnancy
 - Development of a clinically significant laboratory abnormality that requires discontinuation from study drug therapy.
- Insufficient therapeutic effect (see Section [5.8.1](#)).

If a patient is withdrawn from the study, see Section 5.9.

5.8.1 Guidance to Investigators on When to End Study Drug Therapy

Patients who are improving clinically will receive at least 5 days but not more than 7 days of study drug therapy. Study drug therapy should continue until all signs and symptoms of the baseline infection have resolved or improved to such an extent that no further antimicrobial therapy is necessary. Prior to ending study drug therapy, the patients must:

- Be afebrile (temperature $\leq 38^{\circ}\text{C}$ oral or $\leq 38.5^{\circ}\text{C}$ rectally or tympanically) for at least 24 continuous hours, with temperature recorded twice daily
- Have had resolution of all signs and symptoms of CABP, or substantial improvement in signs and symptoms of CABP, such that the Investigator considers antibiotic therapy to be no longer required. Substantial improvement includes a return to pre-CABP baseline levels for patients with decreased pulmonary function (eg, patients with chronic obstructive pulmonary disease).

An insufficient therapeutic effect may be determined prior to the planned EOT visit. This determination will require an assessment of clinical status including the synthesis of symptoms and signs data (both local and systemic) and available laboratory data. Patients who are deemed to have an insufficient therapeutic effect should be considered treatment failures and discontinued from study drug therapy. For the purposes of this study, the following categories and guidelines are provided:

- **Clinical Worsening:** Patients who show systemic or local signs of clinical worsening may be prematurely discontinued from study drug therapy at any time. If the Investigator deems the benefit-to-risk ratio of continuing study drug therapy acceptable, administration of study drug for at least 48 hours is encouraged prior to discontinuation
- **Lack of Clinical Progress:** For patients who are stable, yet do not show signs of improvement, the Investigator is encouraged to continue study drug therapy for a minimum of 72 hours before such patients are considered clinical failures and prematurely discontinued from study drug
- **Resistant Pathogen(s):** In the event that an organism resistant to one or more of the potential study drugs is isolated, the Investigator will determine whether the patient remains on study drug therapy. The Investigator may decide to continue study drug therapy if, in his opinion, there is clear and continuing clinical improvement while on therapy, since the patient may be receiving a treatment to which the organism is susceptible. But, if it is the Investigator's opinion that the patient is not benefiting from the study drug, he may decide to prematurely discontinue study drug therapy and to initiate an alternative and appropriate therapy

5.9 Withdrawal from study

Patients may be withdrawn from the study (ie, investigational product and assessments) at the request of the Principal Investigator or Sponsor. Patients are also, at any time, free to withdraw from study (withdrawal of informed consent) without prejudice to further treatment. Patients should be encouraged to have all EOT assessments performed at the time of withdrawal. Such patients will always be asked about their reason(s) and the presence of AE(s). If possible, they will be seen and assessed by an investigator, and followed up for AE(s) (see Section 6.4.3 and 6.4.4).

Reasons for withdrawal from the study may include, but are not limited to:

- Withdrawal of informed consent
- Significant patient non-compliance, defined as refusal or inability to adhere to the clinical study protocol (CSP) requirements
- Investigator determines that it is in the best interest of the patient to withdrawal from the study due to reasons other than AE

Withdrawn patients will not be replaced.

6. COLLECTION OF STUDY VARIABLES

The investigator will ensure that data are recorded in a timely fashion on the eCRF as specified in the study protocol and in accordance with the instructions provided.

6.1 Recording of data

The Rave Web Based Data Capture (WBDC) system will be used for data collection and query handling. The investigator will ensure that data are recorded on the eCRFs as specified in the study protocol and in accordance with the instructions provided.

The investigator ensures the accuracy, completeness, and timeliness of the data recorded and of the provision of answers to data queries according to the Clinical Study Agreement. The investigator will sign the completed electronic Case Report Forms. A copy of the completed eCRFs will be archived at the study site.

6.2 Data collection and enrolment

Patients meeting selection criteria as specified in Section 4 are eligible to participate in the study. Each patient will undergo baseline procedures as outlined in Table 1 and Appendix H within 24 hours prior to administration of the first dose (Day 1) of study drug. Those patients meeting eligibility criteria will continue Day 1 - EOT, TOC and LFU visits, as appropriate. Procedures for these visits are identified in Table 1 and Appendix H.

6.3 Efficacy

6.3.1 Microbiological Assessments of CABP

6.3.1.1 Sputum Samples for Culture

Obtain adequate sputum samples for culture, Gram's staining, and susceptibility testing at baseline, during the study drug period (Study Day 1 up to Day 7) if medically indicated; at the EOT and TOC visits, if the patient is deemed a clinical failure or if medically indicated; and at the LFU visit if medically indicated and the patient is relapsing. Sputum samples are not obtained at the TOC or LFU visits if the patient was previously deemed a failure. Sputum induction (eg, via nebulisation) should be performed by appropriately trained personnel (eg, a respiratory therapist), if medically indicated. Attempts to collect an adequate sputum sample may be repeated if appropriate. Perform culture and susceptibility testing at the local laboratory and send all isolates that are not contaminants (see list below) to the central laboratory for confirmation of organism identity and susceptibility.

The following organisms are considered sputum contaminants, rather than primary pathogens of CABP, and should not be sent to the central laboratory for confirmation of organism identity and susceptibility:

- Fungi (yeast and molds, eg, *Candida spp.* and *Aspergillus spp.*), unless there is evidence of a secondary fungal infection
- *Enterococcus spp.* or Group D *streptococci*
- *Viridans streptococci*
- *Coagulase-negative staphylococci*
- *Micrococcus spp.*
- *Neisseria spp.* other than *N. meningitidis* and *N. gonorrhoeae*
- *Corynebacterium spp.* and other coryneforms
- *Lactobacillus spp.*
- *Vibrio spp.*
- *Capnocytophaga spp.*
- *Cardiobacterium spp.*
- *Flavobacterium spp.*

Susceptibility testing of all isolates sent to the central laboratory will be performed by broth microdilution tests (to determine the MIC) and Clinical Laboratory Standards Institute (CLSI)

disk diffusion tests. Refer to the Laboratory Manual for specific procedures pertaining to the collection, processing, storage, and shipment of sputum cultures.

6.3.1.2 Pleural Fluid Samples for Culture

Obtain pleural fluid samples for culture, Gram's staining, and susceptibility testing as medically indicated during the study (from baseline to the EOT visit). When pleural fluid cultures are required, collect fluid in one aerobic blood culture bottle and one anaerobic blood culture bottle for a total of two bottles. Perform culture and susceptibility testing at the local laboratory and send **all** isolates to the central laboratory for confirmation of organism identity and susceptibility. Susceptibility testing of all isolates sent to the central laboratory will be performed by broth microdilution tests and Clinical and Laboratory Standards Institute CLSI disk diffusion tests. Refer to the Laboratory Manual for specific procedures pertaining to the collection, processing, storage, and shipment of pleural fluid cultures.

6.3.1.3 Blood Samples for Culture

Obtain blood for culture at baseline and as medically indicated from Study Day 1 to the TOC visit. Repeat blood cultures upon receipt of a positive result (rather than daily) until sterilization is confirmed in those patients with a positive result at baseline (ie, baseline blood culture grows an organism other than those judged to be transient or resident skin flora). Obtain blood for culture at the LFU visit only if medically indicated and the patient is experiencing clinical relapse. Blood for culture is not obtained at the TOC or LFU visits if the patient was previously deemed a failure.

When blood cultures are required, obtain one aerobic bottle and one anaerobic bottle from two separate sites for a total of four bottles. Perform culture and susceptibility testing at the local laboratory and send isolates, other than those judged to be transient or resident skin flora, to the central laboratory for confirmation of organism identity and susceptibility. Susceptibility testing of all isolates sent to the central laboratory will be performed by broth microdilution tests and CLSI disk diffusion tests.

Refer to the Laboratory Manual for specific procedures pertaining to the collection, processing, storage, and shipment of blood cultures.

6.3.1.4 Blood Samples for Serology Testing

Obtain blood samples for serology testing for atypical pathogens at baseline and at the LFU visit.

6.3.1.5 Urine Samples for Antigen Testing

Obtain urine samples for *L. pneumophila* serogroup 1 and *S. pneumoniae* antigen detection at baseline. Results for the Legionella antigen test (a rapid in vitro immunochromatographic assay) must be available before enrolment (see Laboratory Manual). Patients with a positive Legionella antigen test at baseline should not be enrolled in the study.

6.3.2 Clinical Response Definitions

6.3.2.1 Clinical Response at the EOT and TOC Assessments

Clinical outcome assessments (see [Table 5](#)) will be made by the Principal Investigator at the EOT and TOC visits. Clinical response will be classified as cure, failure, or indeterminate based on clinical outcome. A favourable clinical response is “clinical cure”. A clinical failure occurring at an earlier time point will be carried forward to the TOC visit.

Table 5 Clinical Response Assessments at the EOT and TOC Visits

Outcome	Definition
Clinical Cure	Total resolution of all signs and symptoms of pneumonia (ie, CABP), or improvement ^a to such an extent that further antimicrobial therapy is not necessary
Clinical Failure ^b	Any of the following: * Persistence, incomplete clinical resolution, or worsening in signs and symptoms of CABP that requires alternative antimicrobial therapy * Treatment-limiting AE leading to discontinuation of the study treatment regimen, when patient required alternative antimicrobial therapy to treat the pneumonia * Death wherein pneumonia (ie, CABP) is considered causative
Indeterminate	Study data are not available for evaluation of efficacy, for any reason including treatment change prior to completing at least 48 hours of the study treatment regimen; death wherein pneumonia is clearly non-contributory, lost to follow-up, or extenuating circumstances preclude classification as a cure or failure

^a Clinical improvement includes the absence of fever (temperature $\leq 38^{\circ}\text{C}$ oral or $\leq 38.5^{\circ}\text{C}$ rectally or tympanically) for at least 24 continuous hours, with temperature recorded twice daily, in addition to a substantial improvement in signs and symptoms of CABP. Substantial improvement includes a return to pre-CABP baseline levels for patients with decreased pulmonary function (eg, patients with chronic obstructive pulmonary disease).

^b Clinical failures at EOT are carried forward to TOC.

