10. Assess, identify, and record any AEs or SAEs (see Section 6.4), as applicable, contact AstraZeneca
11. Obtain microbiological specimens,
 - If not previously categorized as a treatment failure at EOT and is now a treatment failure, obtain appropriate sputum specimen, and provide to the local laboratory to culture, perform Gram's stain and susceptibility testing. Sputum induction (eg, via nebulisation) should be performed by appropriately trained personnel (eg, a respiratory therapist), if medically indicated. Attempts to collect an adequate sputum sample may be repeated if appropriate. Ensure that all isolates that are not contaminants are sent to the central laboratory for confirmation of organism identity and susceptibility (see Section 6.3.1.1)
 - Obtain pleural fluid specimen only if medically indicated, repeat samples are not required. Collect fluid in one aerobic blood culture bottle and one anaerobic blood culture bottle for a total of two bottles. Provide specimen to the local laboratory to culture, perform Gram's stain and susceptibility testing Ensure that **all** isolates are sent to the central laboratory for confirmation of organism identity and susceptibility (see Section 6.3.1.2)
 - If not previously categorised as a treatment failure at EOT and is now a treatment failure, obtain blood cultures or repeat blood cultures upon receipt of a positive result (rather than daily) until sterilization is confirmed in those patients with a positive result at baseline (ie, baseline blood culture grows an organism other than those judged to be transient or resident skin flora). Obtain one aerobic and one anaerobic bottle of blood from two separate sites for a total of four bottles. Perform culture and susceptibility testing at the local laboratory and send isolates, other than those judged to be transient or resident skin flora, to the central laboratory for confirmation of organism identity and susceptibility. Susceptibility testing of all isolates sent to the central laboratory will be performed by broth microdilution tests and CLSI disk diffusion tests (see Section 6.3.1.4)

Refer to the Laboratory Manual for specific procedures pertaining to the collection, processing, storage, and shipment of all specimens / culture

12. If not previously categorised as a treatment failure, determine patient outcome according to Section 6.3

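### Table 5 does not rank failure against indeterminate for a switch before 48 hours because of worsening, and an indeterminate label leaves open a later score of cure on rescue antibiotics in MITT and mMITT

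*Protocol*

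**What the plan says.** Four parts of the protocol bear on a patient whose pneumonia worsens and who is moved to another antimicrobial before 48 hours.

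- **Section 5.8.1** allows the early stop: "Patients who show systemic or local signs of clinical worsening may be prematurely discontinued from study drug therapy at any time". Giving 48 hours of drug first is encouraged, not required. The section also names the outcome: "Patients who are deemed to have an insufficient therapeutic effect should be considered treatment failures and discontinued from study drug therapy".
- **Section 6.3.2.1, Table 5, failure row** covers "worsening in signs and symptoms of CABP that requires alternative antimicrobial therapy" and sets no minimum time on drug. The **indeterminate row** covers data not available for evaluation "for any reason including treatment change prior to completing at least 48 hours of the study treatment regimen" and makes no exception for worsening. The **cure row** accepts full resolution or "improvement ^a to such an extent that further antimicrobial therapy is not necessary" and does not ask which drug produced it.
- **Carry-forward**, in the same section: "A clinical failure occurring at an earlier time point will be carried forward to the TOC visit". Footnote b to Table 5 likewise speaks only of failures.
- **Follow-up and TOC scoring.** After early discontinuation, section 5.8 says "all other visits occurring after the EOT should be performed". Appendix H section 1.6, step 12, then says: "If not previously categorised as a treatment failure, determine patient outcome according to Section 6.3".

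Section 12.1.1.2 puts anyone who received any study drug in MITT. Section 12.2.2.2 keeps indeterminates in the denominator of the MITT and mMITT cure rates.

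**The concern.** One patient fits two rows of Table 5, and the protocol does not say which row wins. The choice affects what can happen later. A failure at EOT is fixed. An indeterminate at EOT is not carried forward, still attends TOC, and is scored there by the investigator. If a rescue course has worked by then, the patient fits the cure row as written.

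Microbiology follows the clinical score. Under footnote a to Table 7, a patient who was not a failure at EOT and has no culture in the TOC window takes the microbiological outcome from the TOC clinical response. Section 12.1.1.5 expects many or most patients to have no TOC specimen. A TOC cure in mMITT would therefore usually become presumed eradication.

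At stake are the MITT and mMITT secondary analyses, overall success in MITT (which is built on clinical cure), and the MITT part of the superiority test. Early worsening on study drug is direct evidence of lack of effect. If it can be turned into a success by another drug, a real difference between arms in early worsening would be diluted.

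**Working it through.** **1. The plan's own figure.** Section 12.3 gives 85% cure in both arms, a margin of 10%, power of 90% and 77.5% evaluability. Section 12.2 gives a two-sided 95% interval.

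n evaluable per arm = (1.960 + 1.282)² × 2 × 0.85 × 0.15 / 0.10² ≈ 267.9, so 268. Then 268 / 0.775 = 345.8, so 346 per arm and 692 in total. This matches the protocol. The figure rests on CE, so this point does not touch it.

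**2. Is CE affected?** Section 12.1.1.4 requires at least 48 hours of drug for an evaluable failure and at least 72 hours for an evaluable cure. A patient switched for worsening before 48 hours is not evaluable as a failure, and is not evaluable as a cure if later scored as one. (CE does allow an earlier failure for a treatment-limiting adverse event, which is a different case.)

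**3. Does the label alone matter?** The MITT and mMITT clinical cure rate is cures / (cures + failures + indeterminates). Moving a patient between failure and indeterminate changes neither numerator nor denominator. The mMITT favourable microbiological rate works the same way, and Table 10 counts clinical indeterminate as overall failure. The label alone therefore changes only the category counts.

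**4. What does a re-score to cure do?** The protocol gives no early-switch rate, so the inputs here are assumptions. Let s be the proportion of an arm switched before 48 hours for worsening, and q the share of those labelled indeterminate at EOT and then scored cure at TOC.

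- Rise in an arm's MITT cure rate = s × q.
- Shift in the difference (ceftaroline minus ceftriaxone) = q × (s for ceftaroline − s for ceftriaxone).

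Taking 346 per arm as the approximate MITT size, s of 1% to 5% is 3.5 to 17.3 patients per arm.

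| s ceftaroline | s ceftriaxone | q = 0 | q = 0.5 | q = 1 |
|---|---|---|---|---|
| 3% | 3% | 0 | 0 | 0 |
| 3% | 1% | 0 | 1.0 point | 2.0 points |
| 5% | 2% | 0 | 1.5 points | 3.0 points |
| 1% | 3% | 0 | −1.0 point | −2.0 points |

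Entries are shifts in the MITT difference. For example, (5% − 2%) × 1 = 3.0 points. The shift always favours the arm with more early switching.

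For scale, the approximate 95% half-width of the MITT difference at 346 per arm and 85% cure is 1.96 × √(2 × 0.85 × 0.15 / 346) = 5.3 points.

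**The case against.** A reader might infer that the protocol requires these patients to be scored afresh and counted as cures. The text does not support that, and the case against it is substantial.

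- Section 5.8.1 already calls the patient a treatment failure, and Appendix H step 12 uses that same term to decide who is scored at TOC. On this reading the patient has been categorised and is not scored again. Appendix H sections 1.2 to 1.4 also refer to treatment failures on the individual treatment days.
- The CE rule in section 12.1.1.4 asks for 48 hours before a failure is evaluable. That presupposes failures before 48 hours which are merely not evaluable.
- Table 5 governs TOC as well as EOT. A change before 48 hours remains a fact at TOC, so the patient can be read as indeterminate again.
- Presumed eradication depends on the same step, because it needs a TOC cure first.
- The size rests on assumed rates and an assumed imbalance between arms. MITT carries no non-inferiority decision rule and enters formal testing only through superiority.

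All of this stands. It means that the natural reading favours failure, that the range must start at zero, and that the primary conclusion is not at risk. It does not close the gap. No sentence ranks the Table 5 rows, and none prevents a TOC cure for a patient whom the investigator recorded as indeterminate at EOT. Deferring to the statistical analysis plan is only a partial answer. The investigator assigns the response at each visit, across 50 to 56 centres, so inconsistent scoring would already be in the recorded data.

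**Conclusion.** The inconsistency is real: sections 5.8.1 and 6.3.2.1 and Appendix H section 1.6 need to be reconciled. The bias it could cause is possible, not mandated. It needs two further events: the investigator chooses indeterminate at EOT, and then cure at TOC.

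The effect on the MITT difference is zero if these patients stay non-cures or if early switching is equal between arms. It is about 1 to 2 points at an assumed 3% versus 1% with half to all re-scored as cure, and up to about 3 points at an assumed 5% versus 2% with all re-scored. The exposure is confined to MITT and mMITT. The primary CE analysis and the total of 692 do not change. The point deserves correction because closing the gap is cheap, not because the trial's main conclusion depends on it.

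**What to change.** Make two changes to the scoring rules in section 6.3.2.1.

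1. State which Table 5 row prevails when antimicrobial treatment is changed before 48 hours because of worsening or lack of effect. Scoring it as failure is consistent with section 5.8.1. Evaluability for CE stays as set in section 12.1.1.4.
2. Extend footnote b so that a patient who changed antimicrobial treatment for CABP before 48 hours remains a non-cure at TOC in MITT and mMITT, as failure or indeterminate. Such a patient cannot become a clinical cure or presumed eradication on the strength of rescue therapy. Align Appendix H section 1.6, step 12, and footnote a to Table 7 with this.

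These changes concern outcome scoring only and leave the stopping and rescue guidance as it is. The cost is a few lines of text and matching derivation code. MITT and mMITT cure rates may come out slightly lower. The second change also holds as non-cures patients who switched early for reasons unrelated to efficacy. That is conservative for each arm's cure rate and should be stated openly.
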